6.5 Lost to Follow-Up

If a patient fails to provide event information via the study/patient portal 30 days after the start of the trial, the remote coordinator will attempt to contact the participant to ascertain whether or not the participant has had a headache episode or not and if the participant wishes to and/or should continue in the study.

Before a participant is deemed lost to follow up, the investigator or designee must make every effort to regain contact with the participant (where possible, 3 telephone calls and, if necessary, a certified letter to the participant's last known mailing address or local equivalent methods). These contact attempts should be documented in the participant's study record.

Should the participant continue to be unreachable, he/she will be considered to have withdrawn from the study and the study exit form will be completed.

6.6 Test Product Packaging/Handling/Storage/Accountability

- The three-episode supply of test product will be packaged and labeled with ingredients and a study ID number.
- Participants will receive guidance on how to report receipt, store, and use the test product.
- Hawthorne Effect Inc. will support storage and shipment of test product, documentation of test product assignment, and completion of test product accountability.

6.7 Study Management

This study uses a decentralized clinical trial format to foster inclusivity, diversity and accessibility for a broad study population and to ensure efficiencies for enrollment and study data collection. The study will be managed using an end to end virtual clinical trial platform called Hawthorne Effect Study Visit Management Platform which is designed to

make patient participation in clinical trials more accessible and as least burdensome as possible. The Hawthorne Effect platform (www.hawthorne-effect.com) is GCP/ICH/21CFR and HIPAA compliant. Hawthorne Effect uses a network of specialty vetted and trained healthcare professionals, or HEROs who are study investigators, screeners and conduct personalized patient visits for screening and follow-up. For this trial, the Hawthorne Effect study visits will be virtual, and the platform will be used to collect patient reported outcomes and to track screening, enrollment and study compliance.

7 Statistical Considerations

7.1 Study Outcomes Measures

Analysis populations:

The *intent to treat* (ITT) population consists of all participants who are consented, report the onset of a headache, and have taken the study medication at least once. The primary analysis will be in the ITT population.

Primary Endpoint:

The primary endpoint is reduction in headache severity. Patients will be asked to rate headache on the 10-point Mankoski scale at 4 time points: prior to taking the product, 15 minutes after taking the product, 30 minutes after taking the product, and 1 hour after taking the product. The improvement in symptoms from baseline will be evaluated on a pairwise basis separately for each time point. P-values will be computed for the improvement.

There is no control group for the primary analysis.

Secondary Endpoints:

- Time to intervention (taking any product other than the study medication) will be analyzed as a time dependent variable, with the clock starting when the test product is taken.
- A longitudinal analysis will be performed for patients who report on more than one incident of headache.
- Net Promoter Score.
- Comparison against normal behavior will use the paired sample *t*-test.
- An additional data presentation will consist of results from both Treatment and Control

in similar studies appearing in the literature. There will be no formal statistical comparison of results from this study and historical studies.

Secondary endpoints will be gathered on the subjective experience of these participants related to general health, personal experience with the product. The secondary endpoints will be self-reported by the participant on their online portal. There will be a questionnaire related to general health and the subjective experience of the participant administered at baseline and at study exit.

The purpose of the secondary analyses is to investigate the association between various baseline and other measurements and outcomes. These secondary analyses are considered hypothesis generating, and the descriptions are somewhat informal. The trial data may suggest secondary analyses not described here.

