2.2.3 Minimization of Risks

Research participants will be carefully screened to meet enrollment criteria. Participants meeting exclusion criteria will not be enrolled. The study participant informed consent will be presented with clear description of the study requirements and opportunity to have questions answered before enrollment. Once an event occurs review of symptoms will be ascertained at 15 and 30 minutes for up to an hour. Reporting of adverse events will be reviewed routinely and in accordance with regulatory guidelines (21CFR, GCP) by the Principal Investigator. Participants with occurrence of worsening symptoms or adverse events should stop taking the test product and may seek medical attention and exit the study.

3 Study Objectives

Beyond the obvious physical symptoms, lifestyle impact related to tension headaches include decreased work productivity and lost work time [17, 18]. The purpose of the present study is to 1) evaluate the impact of the tension relief test product on the symptoms of tension headaches and functional status in adult men and women who suffer from mild to moderate tension headaches by using the 10-point Mankoski scale [19] and 2) the

subjective experience of these participants related to general health, symptoms of tension headaches, and personal experience with the products.

This will be evaluated based on the primary and secondary endpoints. These endpoints, the analysis populations, and their respective measures are described below. Further details on the methods for measuring the outcomes can be found in the Study Outcome Measures and Analysis Plan sections.

Primary Endpoint:

The primary endpoint is reduction in tension headache severity. Patients will be asked to rate headache on the 10-point Mankoski scale at 4 time points: prior to taking the product, 15 minutes after taking the product, 30 minutes after taking the product and 1 hour after taking the product. The improvement in symptoms from baseline will be evaluated on a pairwise basis separately for each time point. P-values will be computed for the improvement.

There is no control group for the primary analysis.

Secondary Endpoints:

- The time to other intervention will be analyzed.
- A longitudinal analysis will be performed for patients who report on more than one incident of headache.
- Comparison against the participant's normal behavior.
- Net Promoter Score.
- Adverse events will be summarized.

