- An additional data presentation will consist of results from both Treatment and Control
 in similar studies appearing in the literature. There will be no formal statistical
 comparison of results from this study and historical studies.

4 Study Design

The present study will be a prospective, one arm observational study. Patients will begin taking the capsules at the onset of headache symptoms. Onset is defined as the time the participant takes the test product for relief of symptoms. When the participant decides to take the test product, they will report symptoms in the headache diary immediately before to taking the product and rate their symptoms on a 10-point Mankoski scale. After consuming the product, the participant will complete a Mankoski scale at 15 minutes, 30 minutes and 1 hour after taking the product. If needed the participant will be allowed to take alternative medication (alternative treatment) after an hour after taking the product. If alternative medication is taken, the participant will record this in their headache diary.

Study enrollment and management will be de-centralized, where participants do not visit an investigator or a clinic for clinical assessment. The participants will participate in the study at home.

All data collected from during this study will be reported by the patient via eCRFs, eDiary, and other electronic data entries. If a visit is required, it will be conducted via remote contact by telephone.

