4.2 Required Behavior

During the 1 hour after taking the test product, no medication or supplementation (including all CBD products) other than the test product should be taken. Once the 1-hour report has been submitted the patient may take other medications.

Patients are asked to limit the consumption of alcohol beverages to less than or equal to two drinks per day and to abstain from the use of cannabis for the duration of the study.

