- After completing the surveys, the participant will take test product. The participant will take 2 capsules with 6-8 oz. of water per headache episode. With a max of 6 pills per day. (If participant takes 6 pills in 1 day this will be defined as 3 headache episodes and the patient will be exited from the study).
- After taking the test product, the participant will complete a Mankoski pain scale at 15 minutes, 30 minutes, and 1 hour after taking the test product.
- Once the participant's symptoms resolve, the participant will complete the headache diary.
- If the participant takes any other medication outside of the test product, the participant will record this on the headache diary.
- After taking the test product, the participant will be instructed to fill out an Adverse Event form for any side-effects experienced.
- After the first headache episode, the participant will be asked to complete the same process for another 2 headache episodes; however, these are not required.
- If the participant completes the required assessments for a total of 3 headache episodes, they will be prompted, by email, to exit the study.

- If the participant only completes the required assessments for the required 1 headache episode, the participant will be prompted, by email, to complete the study exit form and will be exited from the study on day 60 (60 days from the day of receipt of the test product).
- The sponsor nor Hawthorne Effect Inc. will not make any attempt to collect any unused product.
- Upon receipt of study exit survey and review of completed study forms, participant will receive an Amazon gift card of \$25 via email.

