- **3** Annoying enough to be distracting. Mild painkillers take care of it (Aspirin, Ibuprofen).
- **4** Can be ignored if you are really involved in your work, but still distracting. Mild painkillers remove pain for 3-4 hours.
- **5** Can't be ignored for more than 30 minutes. Mild painkillers ameliorate pain for 3-4 hours.
- **6** Can't be ignored for any length of time, but you can still go to work and participate in social activities. Stronger painkillers (Codeine, narcotics) reduce pain for 3-4 hours.
- **7** Makes it difficult to concentrate, interferes with sleep. You can still function with effort. Stronger painkillers are only partially effective.
- **8** Physical activity severely limited. You can read and converse with effort. Nausea and dizziness set in as factors of pain.
- 9 Unable to speak. Crying out or moaning uncontrollably near delirium.
- 10 Unconscious. Pain makes you pass out.

	Afte	r your	headache	resolved	please com	plete any	of the	following	questions i	if applicabl
--	------	--------	----------	----------	------------	-----------	--------	-----------	-------------	--------------

Did your symptoms resolve completely with the test product? Yes No If yes, time of complete symptom resolution:						
Did you need to take another medication: Yes No						
Medication #1:	Dose:	Time:				
Medication #2:	Dose:	Time:				
Medication #3:	Dose:	Time:				
Did your symptoms resolve completely with taking your medication? Yes No						
After taking medication, time of complete resolution of symptoms:						
Did you experience any side effects after taking the test product? (Y/N) If yes, Please fill out the Adverse Event form.						

13.1.6Appendix F Study Exit Form

symptoms? (y/n)

Study Exit

1.	Pleas	e rate y	our ov	erall ex	perience w	ith th	e test	produc	t.	
0 Poor	1	2	3	4	5 Neutral	6	7	8	9	10 Excellent
1a	. Why?	(free r	espons	e)						
2.	Do yo	ou feel t	hat th	e test p	roduct help	ed w	ith yo	ur head	aches i)
0 Not at	all	2	3	4	5 Neutral	6	7	8	9	10 definitely
3. How likely are you to recommend the test product to your friends or family members?										
0 Not Li	1 kely	2	3	4	5 Neutral	6	7	8	9	10 Extremely Likely
4. Do you feel that the test product helped your body cope with occasional tension and occasional head discomfort?										
0 Not at	all	2	3	4	5 Neutral	6	7	8	9	10 definitely
5.		=	_		you like to sistency, or				-	xperience with the sponse)

6. Did the test product help prevent you from having to take any other medication for your

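### The written event for time to intervention is wider than headache treatment, and the diary records no reason for use, so routine products may be counted as intervention

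*Combined protocol and SAP*

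**What the plan says.** Section 3 (Study Objectives) names the endpoint without defining it: "The time to other intervention will be analyzed". The definition is in Section 7.1: "Time to intervention (taking any product other than the study medication) will be analyzed as a time dependent variable". Time runs from intake of the product. The definition does not limit the event to products taken for the headache.

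Four other places bear on what will be recorded:

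- Section 6.1 is as wide as the definition on medicines: "If the participant takes any other medication outside of the test product, the participant will record this on the headache diary".
- Section 4 (Study Design) is narrower: "If needed the participant will be allowed to take alternative medication (alternative treatment) after an hour after taking the product".
- Section 4.2 bars all other medication and supplements for the first hour, and then: "Once the 1-hour report has been submitted the patient may take other medications".
- Appendix E, in the part completed after the headache resolves, asks "Did you need to take another medication: Yes No". It gives three lines for medication, dose and time, and follows with "Did your symptoms resolve completely with taking your medication". It has no field for the reason and no line for supplements.

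Section 7.3 assigns time-to-event variables to Kaplan-Meier, lists baseline medications among the covariates, and leaves detail to a SAP still to be written. Section 7.1 calls the secondary analyses hypothesis generating.

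**The concern.** A time-to-intervention curve is of interest here because it shows how soon people turn to something else for the headache. Under the wording of 7.1, a scheduled daily tablet taken while the clock runs is an event on the same footing as a pain reliever taken because the test product had not worked.

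Routine products should be expected. The schedule in Section 6.2 collects medications and supplements at baseline, and the one current-medication exclusion listed in Section 5.2 is daily anticoagulant use.

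Two things are at stake. First, the event proportion would be overstated and the times shortened for people on daily products. Second, participants told to record any medication, and then asked whether they needed one, may reasonably answer in either sense, so events may not mean the same thing from one person to the next. Section 7.3 makes covariate analyses the only formal group comparisons. A comparison by baseline medications could therefore pick up routine dosing as well as headache treatment.

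**Working it through.** **The plan's own figure.** None is given for this endpoint. The only power figure is in Section 7.2: 68 patients for 90% power on the primary endpoint, with mean improvement 2 and SD 5. A paired t-test at two-sided 0.05 (assumed; the plan does not state alpha) gives n = 68 with power 0.9016. The figure reproduces and does not involve time to intervention.

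**The texts side by side.**

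| Place | Scope |
|---|---|
| 7.1, event definition | Any non-study product, any reason |
| 6.1, recording instruction | Any other medication, any reason |
| 4, design | Alternative treatment, if needed |
| Appendix E, diary item | Medication that was needed, then whether symptoms resolved with it |

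The first two are wide and the last two narrow. The event time comes from the diary, but the rule that turns a diary entry into an event is the one in 7.1. No text available for review says how to sort entries.

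**Possible size, under assumptions.** The documents give no rescue rate, no share of participants on daily products and no end of the observation window. Assume:

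- R = 30% take a product for the headache within the window;
- a share q = 20% to 60% take one daily product at a uniformly random time, independently of rescue;
- every routine dose is recorded and counted.

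The chance of a routine event in a window of w hours is r = q × w/24. The apparent proportion is 1 − (1 − R)(1 − r).

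Doses due in the barred first hour are either skipped (w = window − 1) or moved to just after minute 60 (w = full window):

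| Window | r, skipped | Apparent | r, moved | Apparent |
|---|---|---|---|---|
| 4 h | 2.5% to 7.5% | 31.8% to 35.3% | 3.3% to 10% | 32.3% to 37.0% |
| 8 h | 5.8% to 17.5% | 34.1% to 42.3% | 6.7% to 20% | 34.7% to 44.0% |
| 24 h | 19.2% to 57.5% | 43.4% to 70.3% | 20% to 60% | 44.0% to 72.0% |

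Example (4 h, moved, q = 60%): r = 0.60 × 4/24 = 0.10, and 1 − 0.70 × 0.90 = 0.37.

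With R = 10% and doses moved, the 4 h range is 1 − 0.90 × 0.967 = 13% to 1 − 0.90 × 0.90 = 19%. The 24 h range is 1 − 0.90 × 0.80 = 28% to 1 − 0.90 × 0.40 = 64%.

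**Doses pushed past the first hour.** These fall where other treatment is first allowed, but they are few: q × 1/24 = 0.8% to 2.5% of participants.

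Both 6.1 and Appendix E have the diary finished once the headache resolves, so the shorter windows may often be the relevant ones.

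**The case against.** The strongest reply is that the diary, not the parenthesis in 7.1, decides what is captured. The diary asks about need, after resolution, and then asks whether the symptoms resolved with that medication. That second question makes sense only for headache treatment, and Section 4 reads the same way. Many participants would therefore report only headache treatment, and a supplement would often not be recorded at all. Product names, checked against the baseline list, let an analyst set aside many routine entries. The endpoint is secondary and single-arm, and the SAP could still supply a rule.

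Most of this stands, and it rules out several stronger readings that a reader might infer:

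- *That the endpoint does not measure need for other headache treatment.* The diary wording and Section 4 steer towards exactly that need.
- *That a vitamin or blood-pressure tablet cannot be told from a pain reliever.* The name is recorded. The unresolved cases are products that could serve either purpose.
- *That nothing else addresses avoidance of other treatment.* Item 6 of the exit form in Appendix F asks, yes or no, whether the product spared the participant other medication for the symptoms.
- *That regular medicine users must show earlier intervention.* This happens only if they report routine doses under a question about need and nobody sorts the entries.

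The reply does not remove the mismatch. Followed as written, 7.1 counts a routine product, and 6.1 tells participants to record routine medicines. Without a stated reason, sorting by name is partial: someone may use the same analgesic routinely and for the headache. Part of the Appendix H insert was not available for review, so a clarifying instruction there cannot be excluded. It would not change the definition in 7.1.

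**Conclusion.** The point holds as a mismatch with a consequence. The event definition and the recording instruction are wider than the design text and the diary item. Applied literally, the definition counts routine products as interventions, and the diary lacks the field needed to separate them reliably.

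Any routine dose that is recorded and counted raises the event proportion. The amount cannot be derived from the documents. Under the stated assumptions, a true 30% becomes about 32% to 37% over 4 hours and about 43% to 72% over 24 hours. The 24-hour figures should not be read as an estimate: they rest on a window the plan does not give, on full recording of routine doses, and at the upper end on 60% daily use in a population described as otherwise healthy.

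The primary analysis and the sample size are unaffected. It is still worth correcting, because the reason for use cannot be reliably recovered after the diaries are complete.

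**What to change.** 1. In 7.1, define the event as the first non-study product taken for the index headache.
2. In Appendix E, add a box to each medication line: *Taken for this headache? Y/N*. Count only the Y entries as events.
3. Keep all other recorded products as concomitant data and check them against the baseline medication and supplement list.
4. Align the wording of 6.1, 7.1 and Appendix E, and carry the rule into the SAP.

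The cost is a sentence in the plan and one tick box per diary line. The downside is slightly more diary burden and reliance on the participant's stated reason.

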6.1 Study Procedures

- Potential participants will review information about the study and complete a screening form.
- During the screening process, the potential participant will be asked questions regarding their symptoms and medical history to ensure that they meet the requirements to participate in this study. Potential participants will also be asked questions to ensure that they do not meet any of the exclusion criteria and meet all of the inclusion criteria.
- After successful screening (participant does not meet any exclusion criteria), participants will review and sign study informed consent.
- Upon verification of signed informed consent, participant will be enrolled into the study.
- At time of enrollment, participant will be given access to the HIPAA compliant study portal.
 - The study portal provides access to study information, signed informed consent form, instructions for product use, frequently asked questions, study surveys, headache diary, and data collection tools.
- Participant shall complete baseline assessments upon access to the portal.
 - O Baseline assessment will include questions regarding the participants' demographics, medications and detailed information regarding their headaches including treatment.
- To ensure that baseline assessments are completed before test product is used by the participant, study materials and study welcome package will be shipped to the participant once the clinical study manager/clinical ops coordinator confirms that the baseline assessment has been completed.
- The welcome package will include an information sheet that will outline instructions for their participation in the trial, the test product, and paper forms of the documents (paper form of study documents will be provided for real time data collection, in the event that the participant cannot log into the study portal to input data).
- Once the participant receives the test product, the participant will log into the study portal to acknowledge the receipt of the test product.
- Study start date will be the reported date of receipt of test product.
- Participant will be sent weekly email reminders that remind them of their participation in the study.
- At the onset of the headache, the participant will start a Headache Diary and complete a 10-point Mankoski pain scale.
 - Onset is defined as the time the participant takes the test product for relief of symptoms.

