6.2 Study Schedule of activities

Assessments	Screening	Consent	Before Receipt of Test Product	Product Received	Event 1	15 Minutes After Event Start	30 Minutes After Event Start	60 Minutes After Event Start
Study Window								
Screening Survey	Х							
Consent		X						
Baseline Survey			Х					
Demographics			Х					
Medications & Supplements			Х					
Acknowledgement of receipt of test product				X				
Headache Diary					X			X
10-point Mankoski Scale					Х	Х	Х	Х
Test Product Consumed					Х			
AE Assessment					X	X	X	X
Study Exit Survey								

Assessments	Event 2	15 Minutes After Event Start	30 Minutes After Event Start	60 Minutes After Event Start	Event 3	15 Minutes After Event Start	30 Minutes After Event Start	60 Minutes After Event Start	Study Exit
Study Window									
Screening Survey									
Consent									
Baseline Survey									
Demographics									
Medications & Supplements									
Acknowledgement of receipt of test product									
Headache Diary	Х			X	Х			X	
10-point Mankoski Scale	X	X	Х	X	X	X	X	X	
Test Product Consumed	Х				X				
AE Assessment	Х	X	Х	X	X	X	Х	X	Х
Study Exit Survey									X

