
13.1.7Appendix G Adverse Event Form

Tension AE document

- 1. Did you experience any side effects after taking the test product? Y/N
 - a. If so, did you experience any of the following
 - o itching, rash, hives, throat/lip/tongue swelling, wheezing
 - low blood pressure, fainting, chest pain, shortness of breath, palpitations, irregular heart beat
 - o severe, persistent nausea, vomiting, diarrhea, or abdominal pain
 - o difficulty urinating, decreased urination
 - o fatigue, appetite loss, yellowing skin/eyes, itching, dark urine
 - severe joint/muscle pain
 - o slurred speech, one-sided weakness of face, arm, leg, vision
 - o abnormal bleeding from nose or gums
 - o blood in urine, stool, vomit,
 - o marked mood, cognitive, or behavioral changes, thoughts of suicide
 - o Other:
- 2. Please give a description of the event
- 3. How soon after taking the test product did you experience the side effect?
- 4. What did you do to alleviate the side effect?
- 5. Did you have to go to the hospital or see a doctor for this side effect?
 - a. Please describe any diagnosis or treatment that they provided.
 - b. If you were seen in the hospital, please upload any discharge paperwork or other documents from the hospital.

13.1.8Appendix H Test Product Insert

Welcome to the Tension Headache Relief Trial!

We appreciate you taking the time to participate in this trial. As you may already know, the aim of this study is to measure the impact the test product has on your headache symptoms. Please take the time to read the following information below to become acquainted with the trial instructions.

Instructions upon Study Product Receipt:

- 1. Please log onto the study portal and acknowledge the receipt by completing the 'Start Form'
- 2. Enclosed in the study bag, please find a 3-episode supply of the tension relief test product.
- 3. You will take the test product the next time you have a headache and need to take something to relieve the discomfort.

Instructions Once Product Intake Begins:

- 1. The next time you have a headache and feel the need to take the test product, you will FIRST start the headache diary (paper forms included in this package).
 - You will complete the date of the episode, the time the episode began, what triggered the headache, type/description of the pain, its location, and record other symptoms (if applicable).
 - REMINDER: DO NOT TAKE ANY OTHER MEDICATION/SUPPLEMENT DURING THE HOUR AFTER TAKE THE TEST PRODUCT.

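### Time to intervention counts any other product as an event, but the diary does not record why it was taken (minor, cheap to fix)

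*Combined protocol and SAP*

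**What the plan says.** - **Event definition (section 7.1).** "Time to intervention (taking any product other than the study medication) will be analyzed as a time dependent variable". The clock starts at the dose of test product. Nothing limits the event to treatment of the headache.
- **Recording rule (section 6.1).** "If the participant takes any other medication outside of the test product, the participant will record this on the headache diary".
- **Diary (Appendix E).** The item reads "Did you need to take another medication", followed by rows for up to three medications with drug, dose and time. The next item is "Did your symptoms resolve completely with taking your medication". There is no field for the reason.
- **Other sources that could help with sorting.** The baseline assessment covers "demographics, medications and detailed information regarding their headaches including treatment", and the schedule in section 6.2 has a baseline line for "Medications & Supplements". The adverse event form (Appendix G) asks "What did you do to alleviate the side effect".
- **Analysis (section 7.3).** Time-to-event variables use Kaplan-Meier, with log-rank or proportional hazards for group comparisons. Baseline medications are named as a covariate. Further detail is left to a later SAP.
- **Status (section 7.1).** "These secondary analyses are considered hypothesis generating, and the descriptions are somewhat informal".
- **One-hour restriction.** Section 4.2, the diary and the visible part of the product insert (Appendix H) bar other medication for an hour after the dose. None of the three states an exception for treating an adverse event.

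**The concern.** The endpoint appears meant to measure how long a participant goes before needing something else for the headache. The stated event is wider. An antacid for reflux, an antihistamine for a rash or a daily prescription tablet, once entered in the diary, is an event on the same footing as an analgesic for the headache. Each such entry makes rescue look more frequent and earlier than it was, so the bias runs against the product.

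There is a second route to error. Section 7.3 relates baseline medications to outcomes. People who take daily medicines have more non-headache tablets to record, so the event definition could itself create an association between baseline medication and early intervention.

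The reason for an intake cannot be recovered reliably later. Drug names, times, the baseline list and Appendix G allow some sorting. They do not settle a dual-use drug such as an analgesic, or a drug missing from the baseline list, and the plan states no sorting rule.

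**Working it through.** The plan gives no rate for this endpoint, so there is no stated figure to reproduce. The only input from the documents is the 97 treated participants in section 5.1. All other rates are assumptions, shown as ranges.

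**1. Effect on the apparent rescue share.** Let q be the true share taking headache rescue and r the share recording a non-headache intake, taken as independent.

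Apparent share = q + (1 − q)r. False events = 97 × (1 − q)r.

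| q | r | Apparent share | False events of 97 |
|---|---|---|---|
| 20% | 2% | 21.6% | 1.6 |
| 20% | 15% | 32.0% | 11.6 |
| 30% | 2% | 31.4% | 1.4 |
| 30% | 15% | 40.5% | 10.2 |
| 40% | 2% | 41.2% | 1.2 |
| 40% | 15% | 49.0% | 8.7 |

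For example, at q = 0.30 and r = 0.15: 0.30 + 0.70 × 0.15 = 0.405, and 97 × 0.70 × 0.15 = 10.2. The range is about 1 to 12 false events.

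**2. Effect on a comparison by baseline medication.** Assume 29 to 48 of the 97 take daily medicines, true rescue is 30% in both groups, and a share w of users record a routine tablet. Testing at 5%, the chance of a significant difference when none exists in headache rescue is as follows. Fisher's exact test is calculated exactly. The log-rank figures are simulated with routine tablets spread evenly over hours 1 to 24 and rescue spread over hours 1 to 4 or 1 to 24.

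| w, recorded over 24 hours | Fisher | Log-rank |
|---|---|---|
| 0% (reference) | 3.6% to 3.8% | 5% |
| 5% | about 5% | 6% to 7% |
| 10% | 9% to 10% | 10% to 12% |
| 25% | 34% to 39% | 30% to 44% |

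**3. The recording window.** The last row needs routine tablets to be recorded over a full day. Section 6.1 has the diary completed once symptoms resolve, and section 6.2 puts the last scheduled diary entry at 60 minutes. Suppose recording ends at 4 or 6 hours (assumed), with rescue over hours 1 to 4. If 25% of users take a routine tablet spread over hours 1 to 24, the share falling inside the window is 0.25 × 3/23 = 3.3% at 4 hours, or 0.25 × 5/23 = 5.4% at 6 hours. The simulated log-rank rate is then about 6% to 7%. With 10% taking such a tablet it is about 5% to 6%. Both are close to the nominal 5%.

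**The case against.** The strongest reply is that the documents, read together, describe headache rescue. Section 4 permits alternative treatment if needed after the hour and has it written in the diary. The diary item speaks of need, and its follow-up asks whether symptoms resolved. The exit form asks whether the product spared the participant other medication for the symptoms. Appendix G asks how soon a side effect began, which can be set against the drug times in the diary. A sorting rule could be written into the later SAP. An any-product event is also simple and needs no self-attributed cause, and its error runs against the sponsor's own product.

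Most of this stands, and it is why the effect is probably small: many routine tablets will not be entered at all. Two things remain. The definition in section 7.1 does not say headache rescue. And a later SAP can narrow the definition but cannot supply a reason that was never collected.

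A reader might infer that the analyses by baseline medication will be seriously misleading. The documents do not support that: the large inflation depends on the 24-hour window and the 25% rate together, and neither is in the plan. A reader might also infer that the one-hour restriction bars participants from treating a reaction. It does not amount to that. Sections 2.2.3 and 6.4 direct participants with adverse events to stop the product and address seeking medical attention, Appendix G presupposes that some will treat a side effect, and part of the insert is not available for review and may cover the point.

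**Conclusion.** The point holds as a minor, inexpensive improvement. The event is defined by any other product and the diary collects no reason, so a recorded non-headache intake counts against the product. On assumed rates of 2% to 15%, a 30% rescue share would read as 31% to 41%. False-positive inflation in the covariate comparison is negligible to modest: about 5% to 7% by log-rank when recording ends within 4 to 6 hours. These sizes rest on assumed rates, on independence of rescue and other intake, and on an assumed recording window.

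The consequence is confined to one secondary endpoint that the plan itself treats as exploratory. The definition of the primary endpoint and the sample size are untouched. The missing exception to the one-hour restriction is a wording point and not a defect on its own.

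**What to change.** 1. **Diary (Appendix E).** Add a reason tick to each medication row: this headache, including worsening / other side effect / regular or other medicine. Headache worsening belongs in the first category because section 6.4.1 lists headache as an anticipated adverse event, and the categories would otherwise overlap.
2. **Section 7.1.** Count only intake for the headache as the time-to-intervention event. Keep the present any-product definition as a sensitivity analysis.
3. **Optional wording (section 4.2, diary reminder, product insert).** Add an exception for treating a side effect other than headache, or on medical advice, with the drug and time recorded. Headache must be excluded, or the clause could be read as allowing an analgesic before the 15-, 30- and 60-minute primary ratings. Flag any episode with analgesic use within the hour in a sensitivity analysis of the primary endpoint.

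The cost is one tick per row, one line of analysis text and, if item 3 is adopted, one clause in three places and one flag. No visits or staff are added. The downside is that the reason is self-reported and will sometimes be wrong; the retained any-product analysis shows how much depends on it. Item 3 may also admit a few episodes with other medication inside the hour. The diary change has to be made before data collection.
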